5.3.1.2.1. Effectiveness of the primary series

Effectiveness of the primary series of mRNA-1273 in those vaccinated participants, will be assessed in participants initially randomized to the mRNA-1273 group (mRNA-1273, vaccinated from July-December 2020, early vaccinated) and those initially randomized to the placebo group (Placebo-mRNA-1273, vaccinated December 2020-April 2021, recent vaccinated) using the PP Primary Series Set. Part A and Part B data after Dose 1 of mRNA-1273 will be included for this analysis, and date of Dose 1 of mRNA-1273 will be used as the reference. The analysis period will be from Dose 1 of mRNA-1273 to earlier of last study participation, booster date, or data cutoff date for efficacy as presented in Table 1.

Using PP Primary Series Set, participants at risk will be those who did not have evidence of prior infection prior to Dose 1 of mRNA-1273, specifically, those in mRNA-1273 (randomized to mRNA-1273 in Part A (baseline/pre-Day 1 SARS-CoV-2 negative is required for inclusion in PP Primary Series Set), and those in Placebo-mRNA-1273 group who were SARS-CoV-2 negative at PDV/unblinding at the start of Part B.

Incidence rates will be provided over the time from Dose 1 of mRNA-1273 to receipt of booster, last study participation, or data cutoff date for efficacy. Incidence rates will also be provided by calendar quarters, as well as by the following time intervals:

- After Dose 1
 - After Dose 1 of mRNA-1273
 - After Dose 1 to before Dose 2 of mRNA-1273
 - After Dose 2 of mRNA-1273
 - Dose 2 to <14 days after Dose 2
 - ≥ 14 days after Dose 2

The last time interval “ ≥ 14 days after Dose 2” of mRNA-1273 may be further partitioned into shorter intervals. For each interval, person-time is calculated for participants at risk at

the beginning of the interval, as the time from the date of the beginning of the time interval to the date of the event/censoring for subjects with an event/censor if the event/censor occurs in the interval; or the time of the interval for subjects who continue to be at risk at the end of the interval. Incidence rate, and 95% CI for incidence rate will be calculated using the exact method adjusting for person-time will be provided by treatment cohort. Number and incidence rates of COVID-19 starting 14 days after Dose 2 of mRNA-1273 will also be provided by calendar quarters.

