Incidence rate will also be provided for the periods defined by emergence and circulation of select variant of interest, e.g. December 2021- data cutoff date (Apr, 2022).

Effectiveness in Part B will be performed, and PP Set will be used with treatment cohorts listed in Table 1 for Part B analysis with similar analysis approach. For Part B, participants at risk at the start of Part B are defined as participants who did not have COVID-19 or SARS-CoV-2 infection and non-positive SARS-CoV-2 status at unblinding/PDV prior to Part B.

5.3.1.2.1.1. Relative Effectiveness of recent vaccinated vs early vaccinated (the Primary Series of mRNA-1273)

Relative effectiveness of recent vaccinated participants (Placebo-mRNA-1273) vs. early vaccinated participants (mRNA-1273) will be assessed using the reduction in incidence rate, calculated as 1- incidence rate ratio (IRR). The 95% CI of reduction in IR will be calculated using the exact method (Poisson distribution) adjusting for person-time.

The above analysis may be performed by calendar quarters and/or time periods.

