5.3.1.2.3. Effectiveness of booster (50 µg mRNA-1273)

The same analysis approach described above will be used to assess relative effectiveness of a booster based on adjudicated COVID-19 starting 14 days after booster using the Per-Protocol Set (Primary Series), participants in PP primary Series Set with no major PD in Part C that may affect critical data or were a known COVID-19 or infection case before Part C or not pre-booster SARS-CoV-2 negative will be excluded from this analysis. Participants received a booster after primary series will be compared with those who did not receive a booster after primary series (treatment group listed below). Number of cases, incidence rates and 95% CI will be provided for each treatment group, and reduction in IR (1-IRR) and its 95% CI will be provided to assess relative effectiveness of a booster after the primary series.

Booster 50 µg	In PP Set, Participants received primary series of mRNA-1273 per schedule in Part A or Part B and received booster 50 µg in Part C Date of reference: date of booster
Not received booster	Participants randomized to/received mRNA-1273 in Part A or B and did not receive booster in Part C

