5.3.1.4. Variant-specific analysis of effectiveness

New SARS-CoV-2 variants have emerged. COVID-19 cases have been and will continue to be sequenced. Summary of variant cases by variants will be provided in adjudicated COVID-19 cases. Effectiveness of vaccine for specific variants will be assessed based on incidence rates if there are sufficient number of variants cases. In this variant-specific analysis, COVID-19 due to the specific variant will be considered as cases, and COVID-19 due to other variants will be censored at the time of documentation of COVID-19.

Analysis of effectiveness against variants may be performed if there are sufficient numbers of variants cases for Primary series, and for booster, respectively.

Number of variant cases, person-time, and incidence rate will be provided. Person-time will be calculated as the total time, for primary series, from dose 1 of primary series; for booster, from booster date, to the earliest of the date of COVID-19, censor, last date of

study participation, or efficacy data cutoff date, whichever was earlier. The incidence rate will be calculated as the number of participants with an event divided by the number of participants at risk and adjusted by person-time (total time at risk) in each treatment group. The 95% CI will be calculated using the exact method (Poisson distribution) and adjusted by person-time.

For primary series, relative effectiveness of recent vaccinated participants (Placebo-mRNA-1273) vs. early vaccinated participants (mRNA-1273) will be assessed using the reduction in incidence rate, calculated as 1- incidence rate ratio (IRR). The 95% CI will be provided for the reduction in IR using the exact method.

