5.3.2.2. Analysis of Other Efficacy Endpoints

Similar analysis methods as for the endpoint of COVID-19 cases (Section 5.3.1) will be applied to the following efficacy endpoints for analysis of primary series based on the PP set, and for Part C based on the Part C PP Set, unless otherwise specified. Start date to define cases will be similar with that for the endpoint of COVID-19 cases.

- Severe COVID-19
- SARS-CoV-2 infection or COVID-19 regardless of symptomatology or severity
- Asymptomatic SARS-CoV-2 Infection
- COVID-19 using a secondary definition of symptoms
- Death caused by COVID-19

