5.6.1.2. Methods Proposed by Lin et al (2021, 2022)

Lin et al (2021, 2022) proposed a method to evaluate long-term COVID-19 vaccine efficacy using Cox regression model with a time-varying vaccine effect

$$\lambda(t|S, X) = \lambda_0(t)e^{(\beta X + I(t > S)\eta(t-S))} \quad (2)$$

Where $\eta(t - S)$ is a piece-wise linear function (e.g. every week).

Here, S denote the time when first dose of vaccination takes place and T denote the time when the endpoint events occurs. Both times are measured in days from the start of the clinical trial. We measure each participant's time to disease from the start of the trial rather than from their time of enrollment because the risk of disease depends on community transmission, which varies over the calendar time. The two timescales are different under staggered enrollment. X denote baseline stratification factor (≥ 18 and < 65 years and not at risk, ≥ 18 and < 65 years and at risk, or ≥ 65 years).

Based on the cox regression, vaccine effect is modeled as a function (η) of time since vaccination ($t-S$) while controlling for the possibly different background infection rate at time t . We may evaluate both the cumulative vaccine effect over the time and instantaneous vaccine effect over time.

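### Recent-versus-early relative effectiveness is fixed as a crude rate ratio over different calendar periods, and the boosted-versus-unboosted comparison has no single workable person-time rule

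*SAP*

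**What the plan says.** All references are to the SAP for Parts B and C unless stated.

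**Recent versus early.** Section 5.3.1.2.1 defines the cohorts as "mRNA-1273, vaccinated from July-December 2020, early vaccinated" and "Placebo-mRNA-1273, vaccinated December 2020-April 2021, recent vaccinated". Each participant's person-time starts at their own first dose of mRNA-1273 and ends at booster, last participation or cutoff. Section 5.3.1.2.1.1 then commits to the measure: "Relative effectiveness of recent vaccinated participants (Placebo-mRNA-1273) vs. early vaccinated participants (mRNA-1273) will be assessed using the reduction in incidence rate", that is, one minus the IRR with an exact Poisson interval. On calendar time it adds only: "The above analysis may be performed by calendar quarters and/or time periods". Section 5.3.1.4 repeats the measure by variant where cases suffice ("For primary series, relative effectiveness of recent vaccinated participants"). Section 5.3.2.2 extends the approach to severe COVID-19, infection and death: "Similar analysis methods as for the endpoint of COVID-19 cases (Section 5.3.1) will be applied to the following efficacy endpoints".

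Calendar-quarter and variant-period results are committed, but only as incidence rates within each cohort. Models on calendar time are in exploratory Section 5.6, where Section 5.6.1.2 measures time from trial start "because the risk of disease depends on community transmission, which varies over the calendar time".

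**Boosted versus unboosted.** Section 5.3.1.2 moves a participant's time from the unboosted to the boosted group on the day of the booster. Table 1 (Section 5.1.5) instead has a fixed group that never received the booster, with the BD-1 visit as reference date. In the text available, that row's period has an end but no start, while the next row starts at the BD-1 visit. Section 5.3.1.2.3 uses fixed groups, gives the unboosted no reference date, and says that participants who "were a known COVID-19 or infection case before Part C or not pre-booster SARS-CoV-2 negative will be excluded from this analysis". Section 3.5.2 makes the BD-1 visit the start of Part C.

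**The concern.** A crude rate ratio compares like with like only if background incidence is flat or both cohorts spread their person-time over the calendar in the same way. Neither can be assumed here. A heavy first winter loads events onto the early cohort and makes recent vaccination look better, which imitates waning. A light first winter or a later wave does the reverse. The exact Poisson interval reflects event-count variability only, so it does not widen to cover this.

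The booster problem is different. Part C begins at the dosing visit, and anyone infected before Part C is removed. If unboosted time before the booster is nonetheless counted, a participant who is boosted later cannot have an event in that time. This is immortal time credited to the unboosted group. It lowers the unboosted rate and works against the booster.

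**Working it through.** The plan gives no expected value, case count or power for either ratio, so there is no stated figure to reproduce. The calculations below assume no true difference, except where a true effect is stated.

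**Recent versus early: inputs.** From the SAP: the two vaccination windows, the end of person-time at booster, and the April 2022 cutoff. Assumed:
- Dose 1 uniform over 27 Jul-15 Dec 2020 (early) and 28 Dec 2020-15 Apr 2021 (recent).
- At risk from 42 days after Dose 1 (28 days to Dose 2, plus 14), so the first recent participant is at risk on 08 Feb 2021.
- Booster uptake rising linearly to 70-90% over 20 Sep-31 Dec 2021; cutoff 05 Apr 2022.
- Incidence multiplied by w over 01 Nov 2020-15 Feb 2021, and by 1-5 from 01 Dec 2021.

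**Formulas.** With daily person-time R(t) and E(t) for the recent and early cohorts and common hazard h(t):

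- Crude IRR = [ΣR·h / ΣR] ÷ [ΣE·h / ΣE].
- Mantel-Haenszel IRR over strata s = Σ(a_s·E_s/T_s) ÷ Σ(b_s·R_s/T_s), where a_s and b_s are recent and early cases and T_s = R_s + E_s.

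**Results.**

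| First-winter multiplier w | Crude IRR |
|---|---|
| 1/3 to 1/2 | 1.11-1.27 |
| 1 | 1.00-1.15 (1.00 if incidence is flat throughout) |
| 2 | 0.83-1.01 |
| 3 | 0.70-0.90 |
| 5 | 0.54-0.74 |

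Over all these scenarios, month-stratified IRR is 0.98-1.00 and quarter-stratified 0.86-1.03. Quarter strata using only time from February 2021 give 0.93-1.01.

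*Hand check.* About 21-22% of early-cohort time precedes the first recent participant at risk. If that 22% carries hazard w and all other time carries 1, crude IRR ≈ 1/(0.78 + 0.22w). This gives 1/1.44 = 0.69 for w = 3, 1/1.88 = 0.53 for w = 5, and 1/0.853 = 1.17 for w = 1/3, in line with the integration when there is no late rise.

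*Interval coverage.* With 300 cases, the nominal 95% interval contains 1.0 in 53% of repetitions when crude IRR is 0.79 and in 52% when it is 1.26. With 100 cases it is 82% for both.

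*Other assumptions.* If both vaccination windows are front-loaded, crude IRR is 0.51-1.27, month-stratified 0.97-1.01 and quarter-stratified 0.80-1.04. A separate calculation with other wave shapes and follow-up gave crude 1-IRR from -64% to +66% under no difference, and 0% with month strata. In that calculation the Section 5.3.1.4 version, whose person-time starts at Dose 1 and so before the variant circulates, gave -31% to -100%.

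**Boosted versus unboosted: inputs.** Assumed: base rate 3% per year, rising 3-5-fold from 01 Dec 2021; uptake as above; boosted time from 14 days after the dose; unboosted time under the moving rule from 20 Sep 2021.

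| Rule | Crude IRR | Month-stratified IRR |
|---|---|---|
| Fixed groups from BD-1, matched visit dates | 1.04-1.05 | - |
| Fixed groups, unboosted visits 30 days later or earlier | 0.96-1.17 | 1.00 |
| Moving groups with the Section 5.3.1.2.3 exclusion | 1.9-4.3 | 1.11-1.50 |
| Moving groups, censoring at infection instead | 1.5-2.2 | 1.00 |

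The first row becomes 1.00 if unboosted time also starts 14 days after the visit. The last month-stratified figure becomes 1.02-1.06 if the rise starts on 15 December.

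With a true booster effectiveness of 50% and 80% boosted, the separate calculation of the third rule gave crude -65% (flat risk) or -70% (fivefold wave), and 11% or 28% with month strata. Starting both groups at BD-1 with month strata returned 50%.

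**The case against.** The SAP is not blind to calendar time. It commits to cohort rates by quarter and by variant period, names an optional quarterly ratio, commits to post-booster rates by calendar month (Section 5.3.1.2.2), and sets out calendar-time models. Quarter strata limited to 2021 remove most of the error. No hypothesis or decision rule depends on these ratios, and the protocol (Synopsis and Section 9.5.1.3) plans long-term efficacy without comparing cohorts. All of this stands and limits the weight of the point. But none of the committed outputs is an adjusted ratio; the only committed ratio is the crude one.

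The sizes rest on assumed waves, uptake and case counts, and Section 5.3.1.2.1.1 does not name a risk interval. Both are true. Counting from Dose 1 instead gives crude 0.60-1.24 and month-stratified 0.99-1.00, so the choice of interval does not remove the problem.

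For the booster, the fixed-group reading of Table 1 and Section 5.3.1.2.3 is coherent and nearly unbiased with matched visits, and the missing start date in Table 1 may have been lost in text extraction. That is fair, and the large figures apply only if the moving-group rule is carried back before Part C. But Section 5.3.1.2.3 refers to the approach described above it, which can be read as including that rule, and nothing says which prevails.

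**Conclusion.** The concern holds and should be fixed. Following Section 5.3.1.2.1.1 as written can produce or hide a recent-versus-early difference in either direction; in the main scenarios the crude IRR runs from 0.54 to 1.27 with no true difference. The mechanism follows from the SAP's own vaccination windows. The size and direction depend on the assumed dates, uptake and incidence pattern.

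For the booster, the bias runs from negligible to large depending on which of three provisions is programmed, so this part is a conflict of definitions rather than a demonstrated error. Calendar adjustment does not settle it, and it does not remove self-selection into boosting, which Section 5.6.2.2 acknowledges.

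**What to change.** **Recent versus early (Sections 5.3.1.2.1.1 and 5.3.1.4).**
- Make the stated estimate a calendar-month-stratified IRR (Mantel-Haenszel or Poisson) with a stratified interval, or a Cox model on calendar time as in Section 5.6.1.2.
- Name the risk interval, and restrict to months in which both cohorts have time at least 14 days after Dose 2.
- For sparse endpoints (severe COVID-19, death), use quarters within those months.
- Keep the crude IRR as descriptive.

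**Boosted versus unboosted (Section 5.3.1.2.3).** Choose one rule and use month strata with it:
- (a) Fixed groups as in Table 1, with unboosted time starting at the BD-1 visit, or 14 days after it to mirror the boosted group, and a statement on participants with no BD-1 visit. The present exclusion fits this rule.
- (b) Moving groups from one stated calendar date, excluding only infections before that date and censoring at infection afterwards, in place of the present exclusion.

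Reword the exclusion sentence, which as written also removes participants who have no major protocol deviation in Part C. State that both ratios are non-confirmatory and that calendar adjustment leaves self-selection in place.

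**Cost.** SAP wording and a stratified analysis of data already held. In the scenarios run, the standard error of log IRR rises 3-18%: for example, with 200 cases, 0.142 to 0.147 (ratio 1.035) or 0.161 to 0.190 (ratio 1.18), because early-cohort time before February 2021 drops out. With only 10 cases, the month-stratified ratio is zero or undefined in 3.4% of repetitions, against 2.6% for the crude ratio; with 20 cases, in about 0% for both.

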5.3.1.2.2. Effectiveness of the booster

For Part C, analysis of COVID-19 after booster, Part C PP Set will be used. For Part C, participants at risk at the start of Part C are defined as participants who did not have COVID-19 and had no SARS-CoV-2 infection prior to Part C , i.e. negative pre-booster SARS-CoV-2 status. Similarly, incidence rates after booster, as well as by calendar months (if feasible), and by time periods of the following time intervals will be provided:

- After Booster

- Booster to <14 days after booster
- ≥14 days after Booster

Person-time, incidence rate, and 95% CI for incidence rate based on the exact method adjusting for person-time will be provided by treatment cohort. Number and incidence rates of COVID-19 starting 14 days after Booster will also be provided by calendar months along with 2 additional time intervals associating with pre-omicron and omicron variant waves: 01-Sep-2021 to 30-Nov-2021 and 01-Dec-2021 to data cutoff date. The non-parametric Kaplan-Meier method will be used to estimate cumulative incidences of time to first occurrence of COVID-19 curve in each treatment cohort.

5.3.1.2.3. Effectiveness of booster (50 µg mRNA-1273)

The same analysis approach described above will be used to assess relative effectiveness of a booster based on adjudicated COVID-19 starting 14 days after booster using the Per-Protocol Set (Primary Series), participants in PP primary Series Set with no major PD in Part C that may affect critical data or were a known COVID-19 or infection case before Part C or not pre-booster SARS-CoV-2 negative will be excluded from this analysis. Participants received a booster after primary series will be compared with those who did not receive a booster after primary series (treatment group listed below). Number of cases, incidence rates and 95% CI will be provided for each treatment group, and reduction in IR (1-IRR) and its 95% CI will be provided to assess relative effectiveness of a booster after the primary series.

Booster 50 µg	In PP Set, Participants received primary series of mRNA-1273 per schedule in Part A or Part B and received booster 50 µg in Part C Date of reference: date of booster
Not received booster	Participants randomized to/received mRNA-1273 in Part A or B and did not receive booster in Part C

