Booster 50 µg	Participants randomized in the blinded phase and received booster 50 µg in Part C Date of reference: date of booster	From dose date in Part C to earlier date of (DBL or data cutoff date for safety, last observed in study ^a).
Not received booster	Participants randomized to/received mRNA-1273 in Part A or B and did not receive booster in Part C Date of reference: date of BD-visit 1	Up to earlier date of (DBL or data cutoff date for safety, last observed in study ^a).
Placebo	Participants randomized to/only received Placebo in Part A or B and did not receive booster in Part C Date of reference: date of BD-visit 1	From BD-visit 1 in Part C to earlier date of (DBL or data cutoff date for safety, last observed in study ^a).
Effectiveness, Immunogenicity of mRNA-1273 primary Series		
mRNA-1273	Participants randomized to mRNA-1273 in the Blinded Phase	From Dose 1 of mRNA-1273 to earlier date of (booster date, DBL or data cutoff date, last observed in study ^a).
Placebo-mRNA-1273	Participants randomized to Placebo and received mRNA-1273 in Part B	
Safety of mRNA-1273 primary Series		
mRNA-1273	Participants received mRNA-1273 in the Blinded Phase	From Dose 1 of mRNA-1273 to earlier date of (booster date, DBL or data cutoff date, last observed in study ^a).
Placebo-mRNA-1273	Participants received Placebo in the Blinded phase and received mRNA-1273 in Part B	

^a last observed in study is the earliest date of study discontinuation, study completion, or death.

All analyses will be conducted using SAS Version 9.4 or higher unless otherwise specified.

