5.3.1.2. Analysis approach for effectiveness of vaccine

COVID-19 will be evaluated using incidence rates. Number of events and incidence rate will be provided in a dynamic approach for each treatment cohort, e.g., a participant without COVID-19 or SARS-COV-2 infection will no longer be considered as “at risk” in the non-booster treatment group from the timepoint when this participant received the booster dose, instead, this participant will be considered as “at risk” in the booster treatment group from that timepoint. Incidence rate will be calculated as the number of

participants with an event divided by the number of subjects at risk adjusted by person-time (years) in each treatment cohort.

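### Under the SAP's dynamic person-time rule, the pre-booster exclusion deletes unboosted infections of participants boosted later but keeps the event-free time of the others, which biases booster effectiveness (1 − IRR) downward

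*SAP*

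**What the plan says.** The comparison is in Section 5.3.1.2.3 of the SAP for Part B and Part C. It introduces no method of its own: "The same analysis approach described above will be used to assess relative effectiveness of a booster". That approach is in the parent section, 5.3.1.2: "Number of events and incidence rate will be provided in a dynamic approach for each treatment cohort". The example given there is this very contrast. An uninfected participant stops being at risk "in the non-booster treatment group from the timepoint when this participant received the booster dose", and is at risk in the booster group from then on. The effect measure is 1 − IRR with a 95% CI, for adjudicated cases from 14 days after the booster, in the PP Primary Series Set.

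Section 5.3.1.2.3 then restricts the set: participants who "were a known COVID-19 or infection case before Part C or not pre-booster SARS-CoV-2 negative will be excluded from this analysis". Section 5.1.3 makes a participant pre-booster positive on any positive RT-PCR or nucleocapsid serology up to the booster date. Section 3.5.2 makes the BD-1 visit the start of Part C.

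Other wording points to fixed groups. The contrast is put as "Participants received a booster after primary series will be compared with those who did not receive a booster after primary series", and the comparator is listed as "Participants randomized to/received mRNA-1273 in Part A or B and did not receive booster in Part C". For that group Table 1 (Section 5.1.5) gives "Date of reference: date of BD-visit 1" and an end of the analysis period, but no start.

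Protocol Section 7.1 allows a booster after COVID-19 once its delay criteria are met. Participants infected while unboosted and boosted later can therefore exist.

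**The concern.** Under the dynamic rule, unboosted time comes from two sources: people never boosted, and people boosted later, up to their booster. The exclusion acts on the second source according to what happened afterwards. Someone who stays uninfected until the booster keeps all of that time in the unboosted denominator. Someone infected during that time and boosted afterwards is not pre-booster negative, and leaves the analysis together with the event. The denominator stays nearly whole while the numerator loses events, so the unboosted rate falls, the IRR rises and 1 − IRR falls.

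This is the only booster contrast by 1 − IRR planned outside the exploratory section, and it would be read as the trial's descriptive answer on relative booster effectiveness.

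**Working it through.** The documents give no incidence, uptake, booster timing or count of infected-then-boosted participants, and no planned figure to reproduce. Everything below is illustrative.

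**Formula.** If a share f of unboosted events is deleted and the person-time is essentially kept, observed IRR = true IRR / (1 − f).

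**Assumptions.** True effectiveness 50% (true IRR 0.5), unboosted hazard constant at 3% per month, a 7-month window, boosters spread evenly over 2 or 4 months (mean wait 1 or 2 months), and 10%, 30% or 50% never boosted. Ignoring depletion, unboosted time per participant is:

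- later boosted: B = (1 − share never boosted) × mean wait
- never boosted: N = share never boosted × 7

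Under a constant hazard, later-boosted people supply B/(B + N) of the unboosted events. So f = B/(B + N) if all their events are deleted, and half of that if half are.

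| Rollout | Never boosted | B | N | f (all) | 1 − IRR (all) | 1 − IRR (half) |
|---|---|---|---|---|---|---|
| 2 months | 10% | 0.9 | 0.7 | 0.5625 | −14% | 30% |
| 2 months | 30% | 0.7 | 2.1 | 0.25 | 33% | 43% |
| 2 months | 50% | 0.5 | 3.5 | 0.125 | 43% | 47% |
| 4 months | 10% | 1.8 | 0.7 | 0.72 | −79% | 22% |
| 4 months | 30% | 1.4 | 2.1 | 0.40 | 17% | 38% |
| 4 months | 50% | 1.0 | 3.5 | 0.222 | 36% | 44% |

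Worked line (4 months, 30% never boosted, all deleted): f = 1.4/3.5 = 0.40; IRR = 0.5/0.60 = 0.833; 1 − IRR = 17%.

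Simulation, which includes depletion, gives −18/32/43% (2 months) and −82/16/36% (4 months) with all deleted. With half deleted it gives 30/42/47% and 22/37/44%. With none deleted it gives about 50% throughout.

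**The fixed-group reading.** Assume 212 days from 01-Sep-2021, boosters over days 20 to 120 (mean wait 70 days), a constant hazard of 0.0003 per day, and a never-boosted clock that starts for everyone on the first day. Later-boosted people now add no unboosted time. People who would have been boosted but were infected first and stayed unboosted fall into the comparator, with their events but little time.

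- 60% uptake: N = 0.4 × 212 = 84.8 and B = 0.6 × 70 = 42. The unboosted rate is inflated by (84.8 + 42)/84.8 = 1.495, so 1 − 0.5/1.495 = 67%.
- 80% uptake: N = 42.4 and B = 56. The inflation is 98.4/42.4 = 2.32, so 1 − 0.5/2.32 = 78% (79% simulated).
- If half of those infected are boosted later and excluded, the simulated results are 60% and 70%. If all are, both are about 50%.

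In the same setting, the dynamic rule with all such infections deleted gives 25% and −16%. The same data can therefore give anything from a negative value to 79%, depending on choices the SAP leaves open.

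**The proposed rule.** Under constant incidence, dynamic person-time without the exclusion returned 49.5% to 50.7% for a true 50%, and 69.6% to 70.5% for a true 70%.

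**The case against.** The strongest objection is that 5.3.1.2.3 lists fixed groups, boosted and never boosted, with the booster date and BD-visit 1 as reference dates. If those labels govern, later-boosted people add no unboosted time and the mechanism disappears. A reader might infer that booster effectiveness is understated outright; the documents support that only under the dynamic rule. That rule is nevertheless the parent section's stated method, its example is boosted versus non-boosted, and 5.3.1.2.3 adopts it. Nor do the labels settle the matter, because Table 1 gives the comparator no start.

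Second, the negative estimates need every such infection to be deleted and only 10% (or, in the other setting, 20%) never boosted. Protocol 7.1 delays boosters after COVID-19 and allows that some may fall outside the study window, so partial deletion is plausible. The exclusion also reaches anyone infected before BD-1 who attends and declines, which pushes the other way. The share is unknown.

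Third, a reader might take the event-free pre-booster time itself as the error. It is not: a correct time-varying analysis keeps it too. The defect is the loss of the matching events. Nor does the bias persist in every calendar period. Once the rollout ends, no pre-booster time of boosted people remains.

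Fourth, Section 5.6.2 already plans Cox models with the booster as a time-varying exposure and without this exclusion stated. They are exploratory and optional, so they do not repair 5.3.1.2.3. Part C's tested objective is immunobridging (Protocol 9.5.3.2), which this point does not touch.

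**Conclusion.** The point stands conditionally. Under the dynamic rule that 5.3.1.2.3 adopts, the exclusion biases 1 − IRR downward whenever any participant is infected while unboosted and boosted later. For an assumed true 50%, under the 7-month assumptions above, the estimate is about 22% to 47% with half of these infections deleted, −82% to 43% with all deleted, and about 50% with none. Under the fixed-group reading this bias is absent, and the estimate is unbiased or too high depending on where the unstated unboosted clock starts. All sizes rest on assumed uptake, timing and incidence. More than a clarification is needed, because the parent section's own method combined with the stated exclusion gives a wrong rate.

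Calendar-time confounding is a separate issue, addressed by the exploratory models in 5.6.2. With an assumed fourfold rise in hazard after 01-Dec-2021 and 60% uptake, the crude dynamic estimate is about 20% for a true 50% even without the exclusion.

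**What to change.** In 5.3.1.2.3, replace the exclusion with an at-risk rule:

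- Enter PP Primary Series participants on a common start date, for example the first booster date in the study, if uninfected on that date.
- Count infections in unboosted time as unboosted events, whether or not the participant is boosted later.
- Move a participant to the booster group at the booster if still uninfected, and remove the first 14 days as in 5.6.2.2.
- Do not use pre-booster status to delete unboosted time or events.

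Align Table 1 and 5.3.1.2 with this rule, including a start of follow-up for the unboosted group. Repair the exclusion sentence at the same time: read literally, it removes participants who have no major deviation.

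The cost is SAP wording and the reprogramming of one analysis. No new data are needed.
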